6.4.3 Criteria for Rechallenge of Amgen Investigational Product After Potential Hepatotoxicity

The decision to rechallenge the subject should be discussed and agreed upon unanimously by the subject, investigator, and Amgen.

If signs or symptoms recur with rechallenge, then the investigational product should be permanently discontinued. Subjects who clearly meet the criteria for permanent discontinuation (as described in [Section 6.2.1.4.4](#)) should never be rechallenged.

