6.2.1.4 Dosage Adjustments, Delays, Rules for Withholding or Restarting, Permanent Discontinuation

6.2.1.4.1 Dose Reduction

Hematological criteria for dose reduction are presented in [Table 4](#) and non-hematological criteria are presented in [Table 5](#). Dose reduction is possible with re-treatment at 1 dose level lower ([Table 5](#))

Table 4. Hematological Criteria for Dose Reduction

CTCAE Grade	ANC ($10^9/L$)	Platelets	Dose Delay ^a	Dose Reduction
Hematological				
0-2	> 1.0	> 50	Continue infusion	No change
3	< 1.0 – 0.5	< 50 – 25	Continue infusion until Investigator assesses toxicity to require interruption	No change
4	< 0.5	< 25	Delay until \leq grade 2	Restart at 1 dose level lower

Table 5. Non-hematological Criteria for Dose Reduction

CTCAE Grade	Dose Delay	Dose Reduction	Comment
Non-hematological			
Infection, cytokine release syndrome, tumor lysis syndrome, diarrhea, hypoxia			
2	Delay until ≤ grade 1	No change	Restart in hospital
3	Delay until ≤ grade 1	Restart at 1 dose level lower	Consider re-escalation if completely recovered and no new toxicity occurred within 7 days of infusion. Permanent discontinuation of study treatment if no recovery within 21 days. Start at the same dose if resolved cytokine release syndrome, infection, tumor lysis syndrome, or hypoxia.
4	Discontinue infusion	Permanent discontinuation of study treatment	-
All other non-hematological toxicities and clinically significant laboratory parameters			
0-2	Continue infusion	No change	Interruption can be considered if deemed necessary by the investigator
3	Delay until ≤ grade 2	Resolution to grade 1 or 2: Restart at 1 dose level lower Resolution to normal within 1 week or a relationship to study drug can be ruled out: No change	Per the Investigator medical discretion to decide whether to continue the infusion for up to 72 hours if toxicity has not occurred during the DLT window and if the toxicity or abnormal labs are responding to treatment or represents an asymptomatic laboratory change. Permanent discontinuation of study treatment if no recovery within 21 days
4	Discontinue infusion	Permanent discontinuation of study treatment	-

ANC = absolute neutrophil count; CTCAE = Common Terminology Criteria for Adverse Events;

DLT = dose-limiting toxicity

^a Applies to all hematologic toxicity that persists for > 24 hours despite appropriate treatment

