6.2.1.4.3 Restarting the Infusion

Treatment may resume if the interruption is \leq 21 days and if:

- The interruption occurred due to other reasons than toxicity (technical or logistic reasons; eg, diagnostic measurements). The infusion can be restarted at the same dose and without additional measures.
- The toxicity has resolved to \leq grade 1. The infusion can be restarted according to guidelines presented in [Table 4](#) or [Table 5](#).
- The toxicity occurred during the DLT period or has resolved to grade 2. The infusion can only be restarted in an individual subject with a clear clinical benefit from treatment after consultation with the sponsor on a case-by-case basis.

Restarting the infusion after a treatment interruption requires care. The start should be performed in the hospital with all infusion day 1 specific measures if the reason for the interruption was other than a technical issue or the interruption was $>$ 24 hours independent of reason. Prophylactic treatment with steroid (eg, dexamethasone) is recommended before restarting of AMG 211 if clinically indicated.

Subjects that have had a treatment interruption during cycle 1 should be given the opportunity to complete a total of 14 or 28 days of infusion even though these may not be DLT evaluable subjects.

Subjects that have had a treatment interruption lasting \geq 48 hours from cycle 2 onwards should re-start treatment as a new cycle.

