6.2.1.4.4 Permanent Discontinuation

A subject will permanently discontinue treatment with investigational product in the event of:

- Dose-limiting or other unmanageable toxicity. If a DLT occurs in a subject with a clear clinical benefit from treatment a restart at a lower dose can be considered if the toxicity has resolved and after consultation with the sponsor.

- Disease progression documented on 2 consecutive imaging assessments separated by at least 4 weeks as defined by modified irRC ([Appendix D](#)). Subjects who show disease progression on a single imaging assessment and who show global clinical deterioration suggesting that no further benefit from treatment is likely should be discontinued from study treatment.
- Withdrawal of subject's consent
- Subject or investigator not compliant with the study protocol
- Occurrence or progression of a medical condition which in the opinion of the investigator should preclude further participation of the subject in the study

All reasons for treatment discontinuation should be clearly and concisely documented in the eCRF. If a subject has not continued to present for study visits, the investigator should determine the reason and circumstances as completely and accurately as possible.

In any case of premature treatment discontinuation, the investigator should make every effort to perform all examinations scheduled for the EOIP and EOS visits. These data should be recorded, as they comprise an essential evaluation that should be performed prior to discharging any subject from the study and to allow for the evaluation of the study endpoints.

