6.4.2 Criteria for Conditional Withholding of Amgen Investigational Product due to Potential Hepatotoxicity

For subjects who do not meet the criteria for permanent discontinuation of Amgen investigational product outlined above and have no underlying liver disease, and

eligibility criteria requiring normal transaminases and TBL at baseline or subjects with underlying liver disease and baseline abnormal transaminases, the following rules are recommended for withholding of Amgen investigational product and other protocol required therapies:

- Elevation of either AST or ALT according to the following schedule:
 - Baseline AST or ALT value: Any AST or ALT elevation: $> 8 \times \text{ULN}$ at any time
 - Baseline AST or ALT value: Any AST or ALT elevation: $> 5 \times \text{ULN}$ but $< 8 \times \text{ULN}$ for ≥ 2 weeks
 - Baseline AST or ALT value: Any AST or ALT elevation: $> 5 \times \text{ULN}$ but $< 8 \times \text{ULN}$ and unable to adhere to enhanced monitoring schedule
 - Baseline AST or ALT value: Any AST or ALT elevation: $> 3 \times \text{ULN}$ with clinical signs or symptoms which are consistent with hepatitis (such as right upper quadrant pain/tenderness, fever, nausea, vomiting, or jaundice).
- OR: TBL $> 3 \times \text{ULN}$ at any time
- OR: ALP $> 8 \times \text{ULN}$ at any time

AMG 211 should be withheld pending investigation into alternative causes of DILI. If the investigational product is withheld, the subject is to be followed according to recommendations in [Appendix A](#) for possible DILI. Rechallenge may be considered if an alternative cause for impaired liver tests (ALT, AST, ALP) and/or elevated TBL is discovered and the laboratory abnormalities resolve to normal or baseline ([Section 6.4.3](#)).

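### The protocol's rules for holding and restarting AMG 211 conflict in three places, and the bar on liver rechallenge cites a section without liver-test criteria

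*Protocol*

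**What the plan says.** Six places in the protocol bear on this. The SAP has no restart rules and only tabulates adverse events leading to withdrawal (10.5.1).

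- **6.2.1.4.1, Table 5.** The residual block is headed "All other non-hematological toxicities and clinically significant laboratory parameters". Its grade 3 entry reads "Resolution to grade 1 or 2: Restart at 1 dose level lower", and also "Resolution to normal within 1 week or a relationship to study drug can be ruled out: No change". The comment column leaves the investigator to "decide whether to continue the infusion for up to 72 hours if toxicity has not occurred during the DLT window", when the event is responding to treatment or is an asymptomatic laboratory change. Failure to recover in 21 days means permanent discontinuation.
- **6.2.1.4.3.** Toxicity that is down to grade 1 or less is sent to Table 4 or Table 5. For toxicity in the DLT period, or down only to grade 2: "The infusion can only be restarted in an individual subject with a clear clinical benefit from treatment after consultation with the sponsor", case by case.
- **6.2.1.4.4.** The reasons for permanent discontinuation are dose-limiting or unmanageable toxicity, progression, withdrawn consent, non-compliance and other medical conditions. The toxicity reason carries an allowance: "If a DLT occurs in a subject with a clear clinical benefit from treatment a restart at a lower dose can be considered", once the toxicity has resolved and the sponsor has been consulted.
- **6.4.1.** Product is stopped permanently on a set combination of bilirubin or INR and transaminase values with no other evident cause.
- **6.4.2.** For subjects outside 6.4.1, withholding is recommended at listed AST, ALT, bilirubin or ALP levels. Rechallenge may be considered if an alternative cause "is discovered and the laboratory abnormalities resolve to normal or baseline".
- **6.4.3.** Rechallenge needs the unanimous agreement of subject, investigator and sponsor. Subjects who clearly meet the "criteria for permanent discontinuation (as described in [Section 6.2.1.4.4](#)) should never be rechallenged".

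**The concern.** A site that holds the infusion for a raised liver test finds two sets of instructions, one general and one for the liver, with different conditions for continuing and for restarting. No sentence says which one applies. Within the general set, the table and the text on restarting also disagree. The one absolute prohibition in the liver section points to a list that contains no liver-test criteria.

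Liver events are foreseeable from the protocol's own background. Section 2.2.5 reports AST, ALT and bilirubin elevations among the DLTs seen in 9 subjects on a related antibody. Section 2.2.4 reports one treatment-related grade 3 ALT increase with AMG 211. Sites that follow different sections could re-expose or withdraw patients with the same event. That is first a safety matter. It also means that the table of adverse events leading to withdrawal (protocol 10.4.2.1.1) would partly reflect which section a site read.

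**Working it through.** No arithmetic applies, so the check sets the rules side by side.

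**1. Table 5 against 6.4.2 and 6.4.3.** The protocol cites CTCAE 4.03 but prints no liver-test thresholds. I therefore did not assign a grade to any multiple of ULN. I took an event that meets 6.4.2 and asked what happens in whichever residual row of Table 5 it falls.

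| Table 5 row | Table 5 | 6.4.2 and 6.4.3 |
|---|---|---|
| Grade 0 to 2 | Continue at the same dose; interruption is the investigator's option | Withhold |
| Grade 3 | Delay to grade 2 or less, or continue up to 72 hours outside the DLT window; restart one level lower at grade 1 or 2 with no cause required; same dose if normal within 1 week or relationship ruled out; 21-day limit | Withhold; rechallenge considered only with alternative cause, values normal or at baseline, and unanimous agreement; no restart dose or time limit given |
| Grade 4 | Permanent discontinuation | Rechallenge left open on the same conditions for an event outside 6.4.1 |

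The two sets differ in every row, so the finding does not depend on how the grades are mapped. They do agree on one path. The event is grade 3, outside the DLT window and not itself a reason for permanent discontinuation. The infusion is withheld, an alternative cause is found and the relationship ruled out, values are normal within 21 days, and all three parties agree.

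**2. Table 5 against 6.2.1.4.3.** This concerns toxicity in general, not only the liver.

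- Resolution only to grade 2: the residual grade 3 row restarts one level lower. Section 6.2.1.4.3 requires clear clinical benefit and sponsor consultation. Table 5 states neither.
- Toxicity in the DLT period: 6.2.1.4.3 applies the same two conditions. In Table 5 the DLT window limits only the 72-hour continuation, not the restart.
- Resolution to grade 1 or less outside the DLT period: no conflict, because 6.2.1.4.3 defers to the tables.

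**3. The reference in 6.4.3.** Section 6.2.1.4.4 contains no ALT, AST, bilirubin, ALP or INR threshold. A liver event can enter it only through a general reason, chiefly dose-limiting or unmanageable toxicity, and that is the reason that carries the restart allowance. So the prohibition is attached to a list with one explicit exception. It is not attached to 6.4.1, where the liver criteria for permanent discontinuation stand.

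**The case against.** The best defence is that a dedicated liver section overrides a residual table row. The language is also soft: continuation under Table 5 is discretionary, treatment under 6.2.1.4.3 may resume, and the 6.4.2 rules are recommended. Appendix A asks for close observation until values are normal or at baseline, which fits 6.4.2. On the reference, a subject within the DLT allowance arguably does not clearly meet the criterion for permanent discontinuation, so 6.4.3 and 6.2.1.4.4 can be read together.

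These readings are reasonable, but the reader has to supply them. No text gives 6.4 precedence, and Appendix A governs monitoring, not restart. Precedence for 6.4 would not repair a reference that sits inside 6.4, nor the disagreement between Table 5 and 6.2.1.4.3, both of which lie outside it.

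Some stronger readings should be resisted:

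- **That subjects meeting 6.4.1 are unprotected.** They are not. Section 6.4.1 already requires permanent discontinuation, and the rechallenge route in 6.4.2 excludes them. What is missing is a correctly attached bar.
- **That one patient faces a countable number of outcomes at a given ALT value.** This needs CTCAE cut-offs that the protocol does not print.
- **That DLT evaluability under the 90% rule, and so replacement, is disturbed.** This is not shown. Section 5.1 keeps subjects who stop for a DLT evaluable, and 10.1.2 excludes only dropouts for reasons other than a related adverse event.
- **That clear benefit cannot be shown in cycle 1.** The protocol does not define benefit by a scan, and 6.2.1.1 leaves the judgment of benefit to the investigator.

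**Conclusion.** The point holds as an internal inconsistency in three parts: Table 5 against 6.4.2 and 6.4.3 for liver tests; Table 5 against 6.2.1.4.3 for resolution to grade 2 and for DLT-period toxicity; and a reference in 6.4.3 that does not reach the liver criteria and meets a restart allowance where it does point. Its size cannot be put in numbers, because the documents do not say how many subjects will be held for liver tests. Section 2.3 names only cytokine release syndrome as an important identified risk, and 2.2.4 reports approximately 32 subjects in this study without a DLT. A reader might infer a class effect on the liver from the background; the documents support only that such events are foreseeable.

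The conclusion assumes that the residual block of Table 5 means what it says about laboratory parameters, and that no document outside the protocol and SAP sets precedence. It should be corrected because it can change what happens to an individual patient. It does not undermine the design or the analysis.

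**What to change.** Reconcile the passages:

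- State in Table 5, 6.2.1.4.3 and 6.4 which of them governs liver tests, for both continuation and restart.
- Align the restart conditions in Table 5 and 6.2.1.4.3 for resolution to grade 2 and for toxicity in the DLT period.
- Check the reference in 6.4.3 against 6.4.1 and correct it, so that the bar attaches to a defined list of criteria.
- Reconcile that bar with the restart allowance in 6.2.1.4.4.

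Which rule should stand is for the sponsor's safety team; this review takes no position. The cost is protocol wording and a letter to sites, with no extra assessments or subjects.

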6.5 Concomitant Therapy

Throughout the study, subjects should be encouraged to remain well hydrated throughout the treatment period.

Investigators may prescribe any concomitant medications or treatments deemed necessary to provide adequate supportive care except for those listed in [Section 6.7](#).

Concomitant therapies are to be collected from informed consent, through the EOS. For

all concomitant therapies collect therapy name, indication, dose, unit, frequency, route, start date, and stop date.

Oxygen administration as supportive measure is permitted during study treatment.

For symptomatic treatment of fever > 38.5°C metamizole as infusion and/or paracetamol, ibuprofen, or acetylsalicylic acid are recommended.

Patients should be closely monitored for any signs and symptoms that may be associated with CRS such as pyrexia, headache, nausea, vomiting, asthenia, hypotension, hypoxia and tachycardia during the initiation of AMG 211 treatment. To mitigate the CRS risk prophylactic treatment with steroids (dexamethasone) is recommended to be administered before the first dose (initial cycle) of AMG 211, and before subsequent cycles of AMG 211 (if clinically indicated). **In the event of CRS, an unscheduled blood sample should be collected to measure cytokine levels.**

- The sponsor may recommend treating subjects with prophylactic dexamethasone according to the following: Dexamethasone at a dose of 8 mg or equivalent corticosteroid will be administered
 - 8 to 12 hours prior to the start of the infusion on day -1
 - 1 hour prior to the start of the infusion on day 1
 - Every 8 to 12 hours after start of infusion on days 1 and 2
- Corticosteroid treatment can be continued if deemed necessary by the investigator and after consultation with the sponsor but doses should be tapered as quickly as feasible. Further variations may be needed that should be discussed and agreed upon in a Dose Level Review Meeting (DLRM).

6.6 Medical Devices

The investigational product must be administered using infusion pumps approved for use by the appropriate regulatory authorities for the country in which the subject is undergoing treatment in both the inpatient and outpatient setting. Investigational product infusion for solution will be prepared in bags for IV infusion and delivered through infusion lines with a 0.2 µm in-line filter that are both compatible with the investigational product as described in the IPIM.

Additional details for the use of the above mentioned medical devices and specific set of device specifications are provided in the IPIM.

Additional medical devices (eg, syringes, sterile needles, alcohol prep pads), that are commercially available are not provided or reimbursed by Amgen (except, if required by local regulation). The investigator overseeing the conduct of the study at each respective institution will be responsible for obtaining these supplies.

6.7 Excluded Treatments and/or Procedures During Study Period

Any anti-tumor therapy other than the investigational product, including cytotoxic and/or cytostatic drugs, hormonal therapy, immunotherapy or any biological response modifiers, any other investigational agent, chronic systemic corticosteroid therapy, other immunosuppressive therapies, or stem-cell transplantation is not allowed.

Radiotherapy is not permitted except for palliation of symptoms and should be discussed with the sponsor's Medical Monitor first. Investigators should ensure that the need for radiation does not indicate progressive disease and that for subjects with measurable disease, radiation is not to the sole site of measurable disease.

The following procedures should also not be undertaken within the timeframes specified prior to enrollment and during the study:

- Participation in an investigational study (drug or device) within 28 days of study day 1. Exception to this criterion is the participation in the optional Imaging Study and all procedures related to this study.
- Major surgery within 28 days of study day 1
- Enrollment into another investigational drug or device study with the exception of participation in the Imaging Study.

6.8 Product Complaints

A product complaint is any written, electronic, or oral communication that alleges deficiencies related to the identity, quality, durability, reliability, safety, effectiveness, or performance of any investigational or non-investigational product(s) or device(s).

Any product complaint(s) associated with an investigational product(s) or non-investigational product(s) or device(s) supplied by Amgen are to be reported according to the instructions provided in the IPIM.

7. STUDY PROCEDURES

7.1 Schedule of Assessments

Table 6. Schedule of Assessments - Cohort 1 (7-day Infusion Cycle 1 and 14-day Infusion for all Subsequent Cycles)

Cycle	SCR	Treatment Period																				Q2 C	EOIP	EO S									
		1					2 and all subsequent cycles ^k																										
Study Day	-14 to -1	1					2					3-5					8					9		15		22							
		Pre-dose	Relative to start of infusion					Relative to EOI					Pre-dose	Relative to start of infusion					Pre-dose	1					2		3-5		8		15		22
Hours			0-1.5	2	3	4	6	8	1	2	4	0	4	96	EOI	0.1	5	2	4	8	2	4		0	6	2	48	16	33	6			
GENERAL ASSESSMENTS																																	
Informed consent	X																																
Hospitalization																																	
Concomitant medications	X	X																										X	X				
Adverse events	X	X																										X	X				
Clinical evaluation ^a	X	X																										X	X				
Vital signs, pulse oximetry	X	X	X ^d	X	X	X	X	X	X	X	X	X	X	X				X	X	X	X	X	X	X	X	X	X	X					
12-lead ECG (triplicate measurement)	X	X																X	X			X	X ^e		X ^e		X ^e		X				
LABORATORY ASSESSMENTS																																	
Serum pregnancy test ^h	X	X																															
Coagulation	X	X																X	X	X							X	X	X				
Hematology, Chemistry	X	X																X	X	X							X	X	X				
Urinalysis	X	X																X	X	X							X	X	X				
Hepatitis serology, HIV	X																																
Anti-AMG 211-antibody		X																X									X	X	X				
DOSING																																	
AMG 211																		X									X						
TUMOR ASSESSMENTS																																	
MRI or CT		X ^g																									X ^f		X ^f				
Tumor markers (eg, CEA)	X	X																X									X ^f	X	X				
BIOMARKER ASSESSMENTS																																	
Circulating tumor cells	X	X																X									X ^f	X	X				
Immune cells	X	X																X	X	X							X	X	X				
Soluble DNA markers	X	X																X	X	X							X ^f	X	X				
Serum markers		X																X	X	X							X ^f	X	X				
Archival tumor tissue	X																																
Tumor biopsy ^b	X																																
PK ASSESSMENTS																																	
AMG 211 PK collection		X	X	X	X	X	X	X	X	X	X	X	X	X	X	X	X	X	X	X	X	X ^e	X ^e	X ^e	X ^e								
sCEA	X	X	X	X	X	X	X	X	X	X	X	X	X	X	X	X	X	X	X	X	X	X ^e	X ^e	X ^e	X ^e								

Footnote defined on next page

CT = computed tomography; EOI = End of Infusion; EOS = End of Study; EOIP = End of Investigational Product; irCR = immune-related complete response; irPD = immune-related progressive disease; irPR = immune-related partial response; irRC = immune-related response criteria; MRI = magnetic resonance imaging; Q2C = Every 2 cycles SCR = Screening

^a Clinical evaluations will include physical examination, Karnofsky Performance Status, and weight. Screening only: medical history and height will also be obtained.

^b Core biopsy is optional at screening if an Archived Tumor Tissue sample is available. If a core biopsy is performed, it must be completed before the start of treatment.

^c Hospitalization for cycle 1 will be for a minimum of 72 hours. Hospitalization for all subsequent cycles will be for a minimum of 48 hours.

^d Vital signs and pulse oximetry will be taken every 30 minutes.

^e Obtained at cycle 2 only.

^f Every 2 cycles (8 to 10 weeks for 4-week cycle) post-therapy initiation. The **MRI or CT** can be obtained earlier if clinical deterioration necessitates an earlier scan. Using the **MRI or CT**, disease will be assessed using the modified irRC. **Both** response (irCR, irPR) and progression (irPD) require confirmation by a repeat, consecutive assessment at least 4 weeks from the date of the first documented assessment, **and the timing of the scan is a medical decision of the managing physician considering the clinical condition of the subject and other laboratory findings**. The confirmatory scan can also be performed at the next scheduled imaging visit **if confirming response**.

^g Tumor evaluation by contrast-enhanced **MRI or CT** of the chest, abdomen, and pelvis will be performed during screening (within 28 days of cycle 1 day 1). Using the **MRI or CT**, disease will be assessed using the modified irRC.

^h Serum pregnancy test will be performed for all females unless surgically sterile or \geq 2 years postmenopausal.

ⁱ **Vital signs and pulse oximetry will be taken every 6 hours.**

^j Radiographic assessment at the end of the study or during the follow-up visits should be performed if the last imaging assessment was performed \geq 6 weeks before the EOS and the subject has not had evidence of confirmed disease progression.

^k Start of treatment at cycle 2 and all subsequent cycles can start +1 day if justified logistical reasons (eg, bank holiday)

Table 7. Schedule of Assessments - Cohorts 2 to 7 (14-day Infusion for all Cycles)

Cycle	SCR	Treatment Period																		Q2C	EOIP	EOS				
		1										2 and all subsequent cycles ^k														
Study Day	-21 to -1		1		2	3-5	8	11	15		16	22	1		2	3-5	8	15	22							
					Relative to start of infusion																					
Hours									Pre-dose	0-1.5	2	3	4	6	8	12	14	20	24	48-96	168					
									Pre-dose	0	6	24	48-96	168	336											
GENERAL ASSESSMENTS																										
Informed consent	X																									
Hospitalization																										
Concomitant medications	X	X																							X	X
Adverse events	X	X																							X	X
Clinical evaluation ^a	X	X																							X	X
Vital signs, pulse oximetry	X	X	X ^d	X	X	X	X	X	X	X	X	X	X	X	X	X	X	X	X ⁱ	X	X	X	X	X	X	
12-lead ECG (triplicate measurement)	X	X																		X	X ^e			X ^e		X
LABORATORY ASSESSMENTS																										
Serum pregnancy test ^b	X	X																		X						
Coagulation	X	X																		X	X			X	X	X
Hematology, Chemistry	X	X																		X	X			X	X	X
Urinalysis	X	X																		X	X			X	X	X
Hepatitis serology, HIV	X																									
Anti-AMG 211-antibody		X																		X				X	X	X
DOSING																										
AMG 211																										
TUMOR ASSESSMENTS																										
MRI or CT	X ^g																							X ⁱ	X ⁱ	
Tumor markers (eg, CEA)	X	X																	X	X			X	X	X	
BIOMARKER ASSESSMENTS																										
Circulating tumor cells	X	X																	X					X ⁱ	X	X
Immune cells	X	X																	X ^e	X ^e	X ^e	X ^e		X	X	
Soluble DNA markers	X	X	X	X	X														X ^e	X ^e	X ^e	X ^e		X ⁱ	X	
Serum markers		X				X													X ^e	X ^e	X ^e					
Archival tumor tissue	X																									
Tumor biopsy ^b	X																		X ⁱ							
PK ASSESSMENTS																										
AMG 211 PK collection		X	X	X	X	X	X	X	X	X	X	X	X	X	X	X	X	X	X ^e	X ^e	X ^e	X ^e				
sCEA	X	X	X	X	X	X	X	X	X	X	X	X	X	X	X	X	X	X	X ^e	X ^e	X ^e	X ^e				

Footnote defined on next page

CEA = carcinoembryonic antigen; CT = computed tomography; ECG = electrocardiogram; EOI = End of Infusion; EOS = End of Study; EOIP = End of Investigational Product; HIV = human immunodeficiency virus; irCR = immune-related complete response; irPD = immune-related progressive disease; irPR = immune-related partial response; irRC = immune-related response criteria; MRI = magnetic resonance imaging; PK = pharmacokinetic; Q2C = Every 2 cycles; sCEA = soluble carcinoembryonic antigen; SCR = Screening

^a Clinical evaluations will include physical examination, Karnofsky Performance Status, and weight. Screening only: medical history and height will also be obtained.

^b Core biopsy is optional at screening if an Archived Tumor Tissue sample is available. If a core biopsy is performed, it must be completed before the start of treatment. Subjects who provide a separate consent may undergo an optional paired biopsy (1-2 weeks prior to cycle 1 day 1 and cycle 1 day 8 to 14) and/or an optional on-treatment biopsy at cycle 1 day 8 to 14.

^c Hospitalization for cycle 1 will be for a minimum of 72 hours. Hospitalization for all subsequent cycles will be for a minimum of 48 hours.

^d Vital signs and pulse oximetry will be taken every 30 minutes.

^e Obtained at cycle 2, 4, 6 and 8 only.

^f Every 2 cycles (8 to 10 weeks for 4-week cycle) post-therapy initiation. The **MRI or CT** can be obtained earlier if clinical deterioration necessitates an earlier scan. Using the **MRI or CT**, disease will be assessed using the modified irRC. **Both** response (irCR, irPR) and progression (irPD) require confirmation by a repeat, consecutive assessment at least 4 weeks from the date of the first documented assessment, **and the timing of the scan is a medical decision of the managing physician considering the clinical condition of the subject and other laboratory findings**. The confirmatory scan can also be performed at the next scheduled imaging visit **if confirming response**.

^g Tumor evaluation by contrast-enhanced **MRI or CT** of the chest, abdomen, and pelvis will be performed during screening (within 28 days of cycle 1 day 1). Using the **MRI or CT**, disease will be assessed using the modified irRC.

^h Serum pregnancy test will be performed for all females unless surgically sterile or \geq 2 years postmenopausal.

ⁱ **Vital signs and pulse oximetry will be taken every 6 hours.**

^j Radiographic assessment at the end of the study or during the follow-up visits should be performed if the last imaging assessment was performed \geq 6 weeks before the EOS and the subject has not had evidence of confirmed disease progression

^k Start of treatment at cycle 2 and all subsequent cycles can start +1 day if justified logistical reasons (eg, bank holiday)

^l One optional tumor biopsy may be provided at cycle 1 after the first or second week of treatment with AMG211, and a separate optional biopsy may be provided at cycle 2 or a subsequent cycle after the first or second week of treatment with AMG211.

Table 8. Schedule of Assessments – 28-day Infusion for all Cycles

Cycle	SCR	Treatment Period														2 and all subsequent cycles ^j																		
		1							29							1			2			3-5			8		15		22		29		36	
Study Day	-21 to -1	Hours	Relative to start of infusion														Relative to EOI							Pre-dose	Relative to start of infusion									
			Pre-dose	0-1.5	2	3	4	6	8	12	14	20	24	48-96	168	EOI	0.5	2	4	8	24	Pre-dose	0	6	24	48-96	168	336						
GENERAL ASSESSMENTS																																		
Informed consent	X																																	
Hospitalization																									X ^c									
Concomitant medications	X	X																								→								
Adverse events	X	X																								→								
Clinical evaluation ^a	X	X																								X	X	X	X	X	X			
Vital signs, pulse oximetry	X	X	X ^d	X	X	X	X	X	X	X	X	X	X	X	X	X	X	X	X	X	X	X ^b	X	X	X	X	X	X						
12-lead ECG (triplicate measurement)	X	X															X					X	X ^e		X ^e					X ^e				
LABORATORY ASSESSMENTS																																		
Serum pregnancy test ^g	X	X																								X								
Coagulation	X	X															X	X	X	X	X	X	X	X	X	X	X	X	X	X	X			
Hematology, Chemistry	X	X															X	X	X	X	X	X	X	X	X	X	X	X	X	X	X			
Urinalysis	X	X															X	X	X	X	X	X	X	X	X	X	X	X	X	X	X			
Hepatitis serology, HIV	X																																	
Anti-AMG 211-antibody		X																								X								
DOSING																																		
AMG 211									X																X									
TUMOR ASSESSMENTS																																		
MRI or CT	X ^f																																	
Tumor markers (eg, CEA)	X	X																	X					X						X				
BIOMARKER ASSESSMENTS																																		
Circulating tumor cells	X	X															X		X		X													
Immune cells	X	X				X											X	X	X	X	X	X	X	X	X ^e		X ^e							
Soluble DNA markers	X	X	X	X	X	X										X	X	X	X	X	X	X	X	X ^e		X ^e								
Serum markers		X			X												X	X	X							X ^e		X ^e	X ^e	X ^e				
Archival tumor tissue	X																																	
Tumor biopsy ^b	X																X ^k															X ^k		
PK ASSESSMENTS																																		
AMG 211 PK collection		X	X	X	X	X				X	X	X	X	X	X	X	X	X	X	X	X	X	X	X ^e	X ^e	X ^e	X ^e	X ^e	X ^e	X ^e				
sCEA	X	X	X	X	X	X			X	X	X	X	X	X	X	X	X	X	X	X	X	X	X	X ^e	X ^e	X ^e	X ^e	X ^e	X ^e	X ^e				

Page 1 of 2

Footnote defined on next page

CEA = carcinoembryonic antigen; CT = computed tomography; ECG = electrocardiogram; EOI = End of Infusion; EOS = End of Study; EOIP = End of Investigational Product; HIV = human immunodeficiency virus; irCR = immune-related complete response; irPD = immune-related progressive disease; irPR = immune-related partial response; irRC = immune-related response criteria; MRI = magnetic resonance imaging; PK = pharmacokinetic; Q2C = Every 2 cycles; sCEA = soluble carcinoembryonic antigen; SCR = Screening

^a Clinical evaluations will include physical examination, Karnofsky Performance Status, and weight. Screening only: medical history and height will also be obtained.

^b Core biopsy is optional at screening if an Archived Tumor Tissue sample is available. If a core biopsy is performed, it must be completed before the start of treatment. Subjects who provide a separate consent may undergo an optional paired biopsy (1-2 weeks prior to cycle 1 day 1 and cycle 1 day 8) and/or an optional on-treatment biopsy at cycle 1 day 8.

^c Hospitalization for cycle 1 will be for a minimum of 72 hours. Hospitalization for all subsequent cycles will be for a minimum of 48 hours.

^d Vital signs and pulse oximetry will be taken every 30 minutes.

^e Obtained at cycle 2, 4, 6 and 8 only.

^f Tumor evaluation by contrast-enhanced **MRI or CT** of the chest, abdomen, and pelvis will be performed during screening (within 28 days of cycle 1 day 1). Using the **MRI or CT**, disease will be assessed using the modified irRC.

^g Serum pregnancy test will be performed for all females unless surgically sterile or \geq 2 years postmenopausal.

^h **Vital signs and pulse oximetry will be taken every 6 hours.**

ⁱ Start of treatment in cycle 2 and all subsequent cycles can start +1 day if justified logistical reasons (eg, bank holiday)

^k One optional tumor biopsy may be provided at cycle 1 after the first or second week of treatment with AMG211, and a separate optional biopsy may be provided at cycle 2 or a subsequent cycle after the first or second week of treatment with AMG211.

Table 8. Schedule of Assessments – 28-day Infusion for all Cycles

Cycle	Treatment Period		
	Q2C	EOIP	EOS
Study Day			
Hours			
GENERAL ASSESSMENTS			
Informed consent			
Hospitalization			
Concomitant medications		X	X
Adverse events		X	X
Clinical evaluation ^a		X	X
Vital signs, pulse oximetry		X	X
12-lead ECG (triplicate measurement)			X
LABORATORY ASSESSMENTS			
Serum pregnancy test ^g			
Coagulation		X	X
Hematology, Chemistry		X	X
Urinalysis		X	X
Hepatitis serology, HIV			
Anti-AMG 211-antibody		X	X
DOSING			
AMG 211			
TUMOR ASSESSMENTS			
MRI or CT	X ⁱ		X ⁱ
Tumor markers (eg, CEA)		X	X
BIOMARKER ASSESSMENTS			
Circulating tumor cells	X ⁱ	X	X
Immune cells		X	X
Soluble DNA markers	X ⁱ	X	X
Serum markers			
Archival tumor tissue			
Tumor biopsy ^b			
PK ASSESSMENTS			
AMG 211 PK collection			
sCEA			

Page 2 of 2

Footnote defined on next page

CEA = carcinoembryonic antigen; CT = computed tomography; ECG = electrocardiogram; EOI = End of Infusion; EOS = End of Study; EOIP = End of Investigational Product; HIV = human immunodeficiency virus; irCR = immune-related complete response; irPD = immune-related progressive disease; irPR = immune-related partial response; irRC = immune-related response criteria; MRI = magnetic resonance imaging; PK = pharmacokinetic; Q2C = Every 2 cycles; sCEA = soluble carcinoembryonic antigen; SCR = Screening

^a Clinical evaluations will include physical examination, Karnofsky Performance Status, and weight. Screening only: medical history and height will also be obtained.

^b Core biopsy is optional at screening if an Archived Tumor Tissue sample is available. If a core biopsy is performed, it must be completed before the start of treatment. Subjects who provide a separate consent may undergo an optional paired biopsy (1-2 weeks prior to cycle 1 day 1 and cycle 1 day 8 to 28) and/or an optional on-treatment biopsy at cycle 1 day 8 to 28.

^g Serum pregnancy test will be performed for all females unless surgically sterile or \geq 2 years postmenopausal.

ⁱ Every 2nd cycle (10 to 12 weeks for 6-week cycle) post-therapy initiation. The **MRI or CT** can be obtained earlier if clinical deterioration necessitates an earlier scan. Using the **MRI or CT**, disease will be assessed using the modified irRC. **Both** response (irCR, irPR) and progression (irPD) require confirmation by a repeat, consecutive assessment at least 4 weeks from the date of the first documented assessment, **and the timing of the scan is a medical decision of the managing physician considering the clinical condition of the subject and other laboratory findings**. The confirmatory scan can also be performed at the next scheduled imaging visit **if confirming response**.

^j Radiographic assessment at the end of the study or during the follow-up visits should be performed if the last imaging assessment was performed \geq 6 weeks before the EOS and the subject has not had evidence of confirmed disease progression

